4.2.1.2 Evaluation of Efficacy

Primary Efficacy: Overall/event-free survival (survival without need for BMT or PEG-ADA).

Overall/event-free survival will be determined for each subject by 12 months where failure is defined by one of the following endpoints: death; reinstatement of PEG-ADA; or performance of an allogeneic BMT.

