11.7.3 Immunogenicity or Efficacy Review

1. Safety (absence of grade III-IV SAE)
2. Overall/event-free survival (survival without need for HSCT or PEG-ADA ERT)
3. Gene-marking by lineage
4. Erythrocyte ADA enzyme activity
5. Absolute lymphocytes on CBC
6. Absolute number T, B, NK lymphocytes in peripheral blood
7. Lymphocyte proliferation to mitogen (PHA) and antigens (tetanus toxoid)
8. Quantitative immunoglobulins by class (IgG, IgA, IgM)
9. Antibody responses [isohemagglutinins, tetanus toxoid, polyribosylphosphate (PRP)]

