5.1 Primary Endpoints

The primary endpoints are:

- Safety: the incidence and severity of serious adverse events (SAEs)
- Efficacy: overall and event-free survival at 12 months, where events are death, reinstitution of PEG-ADA therapy and performance of an allogeneic BMT.

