8.3.1 Primary Efficacy Endpoints

8.3.1.1 Overall Survival at 12 Months

Overall survival will be evaluated using the time in months from transplant to either the subject's death or their last evaluation calculated as:

12*(date of death/last evaluation – date of transplant)/365.25,

or, for HSCT control subjects for whom the dates were not recorded, as:

age in months at death/end of follow-up - age in months at transplant.

The number (%) of subjects who were still alive at 12 months post-transplant will be summarised. For the purpose of this analysis, any subject who withdrew from the study prior to 12 months, who was known to be alive at the last evaluation, will have a status of "unknown". The proportion and exact 95% confidence interval (CI) for survivors at 12 months post-transplant will be calculated for the OTL-101 treated and each of the HSCT control groups along with the difference in proportions (with 95% CI) between the OTL-101 treated and each of the control groups, excluding those with unknown status.

Final Version 4.0 Page 17 of 27

Overall survival in each treatment group will also be presented using a Kaplan-Meier curve for time to death. For the purpose of this analysis, any subject who withdrew from the study prior to 12 months and was known to be alive at the last evaluation will be censored at the date of their last evaluation. If appropriate, the proportion alive at 12 months and the associated 95% confidence interval will be estimated for each treatment group from the Kaplan-Meier curve along with the median survival time (and interquartile range), if they can be estimated from the data.

If there is at least one event in each group, the log-rank test will be used to compare the difference in survival curves between the OTL-101 treated subjects and each of the HSCT control groups.

In addition, a Bayesian analysis will be carried out. The prior distribution for the rate of survivors in each treatment group will be set to Beta(α =1, β =1) (a conservative non-informative prior). The number of survivors in each group (X) will be estimated and the posterior distribution for the rate of survivors in each group will be updated to Beta(α =1 + X, β =1 +N - X), where N is the total number of subjects in the group. Histograms will be presented for the posterior distributions for each treatment group.

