8.3.1.2 Event-free Survival at 12 Months

Event-free survival will be evaluated using the time in months from transplant to either the first event or their last evaluation calculated as:

12*(date of event/last evaluation – date of transplant)/365.25,

or, for HSCT control subjects for whom the dates were not recorded, as:

age in months at death/end of follow-up - age in months at transplant.

For the purpose of this analysis, the events of interest are:

- death:
- reinstitution of PEG-ADA ERT;
- requirement for a second transplant.

Event-free survival will be summarized in the same way as overall survival described in Section 8.3.1.1.

Final Version 4.0 Page 18 of 27

In addition, if there are any events (other than death), the time to each event will be summarized in a similar manner to the overall event-free survival.

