8.3.2 Secondary Efficacy Endpoints

8.3.2.1 Overall and Event-free Survival at 24 Months

Overall and event-free survival at 24 months will be summarized in the same way as for the analyses at 12 months described in Sections 8.3.1.1 and 8.3.1.2.

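### Event-free survival counts a restart of PEG-ADA but not a failure to stop it, so a survivor never taken off the drug scores as a success

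*Protocol*

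**What the plan says.** Protocol 4.2.1.2 describes primary efficacy as "survival without need for BMT or PEG-ADA", and Protocol 11.7.3 uses nearly the same description, "survival without need for HSCT or PEG-ADA ERT". The rule that decides who fails follows in 4.2.1.2: "failure is defined by one of the following endpoints: death; reinstatement of PEG-ADA; or performance of an allogeneic BMT".

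The SAP repeats the rule. Section 5.1 has "where events are death, reinstitution of PEG-ADA therapy and performance of an allogeneic BMT". Section 8.3.1.2 lists "reinstitution of PEG-ADA ERT" beside death and the requirement for a second transplant. Protocol Appendix H, item 6, defines the event for the HSCT comparison as a need to return to PEG-ADA or a second transplant.

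On analysis, SAP 8.3.1.2 states "Event-free survival will be summarized in the same way as overall survival described in Section 8.3.1.1", and 8.3.2.1 states "Overall and event-free survival at 24 months will be summarized in the same way as for the analyses at 12 months". The event list therefore feeds the exact proportions, the Kaplan-Meier curves and the Beta(1,1) posteriors at both time points.

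On stopping the drug, Protocol 1.1 and 4.1 give day +30 plainly. Protocol 6.4.1, 7.4 and Appendix B make the stop conditional on the patient being free of active infection and other serious medical problems. None sets a latest date for a deferred stop.

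**The concern.** Need for PEG-ADA and restarting PEG-ADA are different states. A patient who stays on the drug throughout needs it at least as much as one who came off and went back, yet only the second is an event. A programmer working from SAP 8.3.1.2 would code the first as event-free.

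What is at stake is the meaning of a primary endpoint. As written, it can count PEG-ADA-dependent survivors as successes. With 20 treated subjects, each classification is worth 5 percentage points. The comparator is retrospective and has no protocol-driven stop, so the two groups may not have had the same chance of being off the drug and thus at risk of a restart.

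**Working it through.** **1. Is the gap real?** The places that define the PEG-ADA component, side by side:

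| Place | What counts |
|---|---|
| Protocol 4.2.1.2, description | any need |
| Protocol 11.7.3 | any need |
| Protocol 4.2.1.2, failure rule | restart |
| SAP 5.1 and 8.3.1.2 | restart |
| Protocol Appendix H, item 6 | return |

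**2. Does another rule catch a never-stopper?**
- The 6-month criteria (Protocol 7.5) and 12-month criteria (6.4.1) act by restarting the drug, so they create no event in someone still on it.
- The subjects in Protocol 7.3 who remain on PEG-ADA are withdrawn without receiving OTL-101, so they are outside the efficacy population.
- SAP 8.3.3.1 foresees subjects in both groups who are not yet off the drug, but censors them in a separate time-to-withdrawal analysis.
- SAP 8.2.16 counts controls on enzyme replacement after transplant, descriptively only.

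None of these feeds event-free survival.

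**3. Can the state arise?**
- *OTL-101.* Only if the day +30 stop is deferred and still not made at the landmark, through 9 scheduled monthly visits to month 12 (1, 2, 3, 4, 5, 6, 8, 10, 12) or 13 to month 24 (adding 15, 18, 21, 24).
- *Controls.* No stop rule applies. In Protocol 2.1.3.1, Table 1, 14 of 19 haploidentical recipients at Duke were alive but only 7 were alive with T-cell engraftment, leaving 14 − 7 = 7 survivors without it. Item e of that section calls non-engraftment a major problem in unconditioned haploidentical transplants. Table 1 comes from a 2006 conference, so it only partly overlaps the control window from 2000 onward. It gives neither enzyme use nor second transplants.

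**4. Size for OTL-101.** The Clopper-Pearson method first reproduces the plan's own figure: Protocol 11.4 gives 12% precision for one failure in 20, and (99.87 − 75.13)/2 = 12.4. The protocol's companion 7% for 20/20 does not match the two-sided half-width, (100 − 83.2)/2 = 8.4. That is a separate matter.

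The SAP posterior mean is (1 + X)/(2 + N), with N = 20.

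| Scored event-free | Rate | Exact 95% CI | Posterior mean |
|---|---|---|---|
| 20/20 | 100% | 83.2 to 100 | 21/22 = 95.5% |
| 19/20 | 95% | 75.1 to 99.9 | 20/22 = 90.9% |
| 18/20 | 90% | 68.3 to 98.8 | 19/22 = 86.4% |

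**5. Size for controls.** Appendix H identifies 25 GOSH and 10 Duke patients, 35 in all, so one never-stopper is worth 100/35 = 2.9 points of the all-control rate. The size of the primary control group (no matched related donor) is not given. If it were 15 to 25, one subject would be worth 6.7 to 4.0 points.

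**6. Effect on the comparison, illustration only.** Assume 20/20 on OTL-101 and a control result of 12/15 or 20/25. The posterior probability that the OTL-101 rate exceeds the control rate is then:

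| Reclassified as failures | Control 12/15 | Control 20/25 |
|---|---|---|
| none | 0.972 | 0.978 |
| one OTL-101 subject | 0.902 | 0.913 |
| one control | 0.990 | 0.989 |
| one in each group | 0.957 | 0.951 |

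The first 12/15 entry can be checked by hand: 1 − (13·14·15·16)/(34·35·36·37) = 0.972. The shift goes down or up according to which group holds the never-stopper.

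**The case against.** The best case against has four parts.

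*The state is close to hypothetical.* For OTL-101 a temporary deferral would have to last a year or more under close follow-up, and no such subject is shown. For controls, the one explicit ADA-SCID survivor on PEG-ADA in Protocol 2.1.3.1 had rejected two transplants, so is already an event through the second-transplant component. A control restarted after any gap is also already counted. This stands as a limit on weight. It does not remove the conflict in wording.

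*Such subjects would be visible.* The analyses in SAP 8.3.3.1 and 8.2.16, and the by-subject listings in Protocol 11.6.1, would show them beside the endpoint table. This is true, but the headline rate would still count them as successes.

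*Counting a safety-driven deferral as failure is a clinical judgement*, since engraftment may be good. This stands, and the sponsor should confirm the judgement. The endpoint as described is nonetheless freedom from the drug, which such a patient has not shown.

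*Interim results were already known.* Protocol 2.1.6.2 reports enrolment closed and 100% event-free survival in 18 evaluable patients. A change to a primary event therefore has to be recorded openly as made after those data.

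A reader might go further and infer that one classification decides whether the log-rank test is run, because SAP 8.3.1.1 says "If there is at least one event in each group, the log-rank test will be used to compare the difference in survival curves". The documents do not support making this part of the case. Protocol 11.6.2.4.1 plans the log-rank comparison with no event-count condition, and the intervals, curves and posteriors are produced either way. A reader might also infer that the interim 100% conceals PEG-ADA-dependent patients, or that the gap favours OTL-101. Nothing in the documents shows either.

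**Conclusion.** The point holds as a minor one. The event lists require a restart, no other rule catches a survivor who never stopped, and the resulting classification contradicts the endpoint's own description. The gap can only raise event-free survival, in either group.

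How many subjects are affected is not given and may be none. The OTL-101 route is narrow, and the control route is possible but undocumented. One affected OTL-101 subject moves the rate by 5 points. One control moves the all-control rate by 2.9 points, and the primary-control rate by 4.0 to 6.7 points if that group has 25 to 15 members. The net direction of bias in the comparison is unknown.

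**What to change.** In Protocol 4.2.1.2 and SAP 5.1 and 8.3.1.2, define the PEG-ADA event as: *reinstitution of PEG-ADA, or PEG-ADA never stopped and still being received at the landmark*. Bring Appendix H, item 6, into line.

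- Apply the rule identically to OTL-101 subjects and HSCT controls, for the 12- and 24-month proportions and Beta posteriors. A first stop at month 13 with no restart is then a failure at 12 months and event-free at 24; a footnote should say so.
- Keep the main Kaplan-Meier curve on dated events. Add one sensitivity curve that counts never-stoppers as failures, with the date convention stated. If they are dated at each analysis's landmark, the 12- and 24-month versions of that curve can differ at month 12, which is why this should not be the main curve.
- Subjects lost before the landmark follow the existing unknown-status and censoring rules of SAP 8.3.1.1.
- Confirm that post-transplant enzyme replacement is captured for GOSH controls. Appendix H lists it for Duke but only prior PEG-ADA for GOSH. The existing restart event needs the same data.
- Record the change as a clarification made after interim event-free survival was known.

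Cost: one clause in each place, one extra curve and a check of the GOSH case report form. SAP 8.2.16 and 8.3.3.1 already plan to use the enzyme data. Event-free survival may come out slightly less favourable in either group.

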4.2.2 Secondary Endpoints

The secondary endpoint is overall survival and event free survival at 24 month.

The other Secondary efficacy falls under the following outcomes or categories:

1. Efficacy of gene transfer/engraftment of HSC
2. ADA expression, enzyme activity and detoxification
3. Effects on ADA reconstitution on immune phenotype and function (the need for IgRT will be assessed under this category)
4. Immune reconstitution
5. Infection rates

1. Efficacy of gene transfer/engraftment of HSC

Secondary Efficacy Endpoint 1: Determine the frequency of gene marking in PB cells.

To assess the efficacy of stem cell transduction/engraftment by serial examination of peripheral blood lymphocytes and myeloid cells to quantify the percentages of cells containing the ADA cDNA by quantitative DNA-PCR. We will obtain serial samples of peripheral blood and fractionate the leukocytes on ficoll-hypaque to obtain peripheral blood mononuclear cells (PBMC) and granulocytes. Genomic DNA isolated from each cell population will be assayed for the frequency of cells containing the EFS-ADA vector by quantitative PCR (qPCR). If sufficient cells are available, then the PBMC cells may be sub-fractionated by immunoaffinity or FACS sorting into T

cells (CD3+), B cells (CD19+), NK cells (CD16+/CD56+) and myeloid cells (CD13+/CD14+, or CD33+) and DNA from these cell sub-populations assayed by qPCR for vector marking.

The presence of transduced peripheral blood leukocytes will demonstrate the transduction and engraftment of the manipulated CD34+ cells. Absence of transduced cells will indicate failure of transduction and/or engraftment. Because of the rapid turnover of mature myeloid cells, the continued presence (>6 months) of transduced granulocytes and monocytes, will be taken as evidence of transduced/engrafted long-lived stem cells. Increased levels of transduced T and B lymphocytes, above the level of transduced myeloid cells, will indicate a selective advantage to T and B progenitors expressing the normal ADA gene.

Secondary Efficacy Endpoint 2: Quantitate clonal diversity of vector integrants.

The clonal diversity will be quantitated and used as an index of the numbers of vector transduced HSC that engrafted in the subjects. The number of retroviral vector (for the prior and current trials) and lentiviral vector (for the proposed trial) integration sites will be amplified by a modified nrLAM-PCR protocol ([Paruzynski, et al, 2010](#)) and sequenced via Illumina GAIIx high-throughput sequencers. Custom software code has been written to process raw sequence reads and determine the genomic positions of integration sites. We expect to identify >1x 10⁵ integration sites per experiment, which will lend significant statistical power to downstream analysis.

2. ADA expression and enzyme activity

Secondary Efficacy Endpoint 3: ADA enzyme activity in erythrocytes.

ADA enzymatic activity in erythrocytes will be measured by [name]'s CLIA-certified laboratory at Duke University, Durham, North Carolina as a clinical test. Attainment (yes/no) of levels compared to the normal reference range (63±41 nmol/h/mg) will be evaluated.

Secondary Efficacy Endpoint 4: Total adenine nucleotides in erythrocytes.

The levels erythrocyte deoxyadenosine nucleotides will be determined at each time point (at the laboratory of [name], Duke University). The level of deoxyadenine nucleotides in erythrocytes provides an indirect assessment of systemic detoxification by ADA enzyme activity. While not a primary study end-point, these parameters will be measured to provide additional information on the effects of the gene transfer.

3. Effects on ADA reconstitution on immune phenotype and function

These immunological assays will provide a laboratory assessment of immune function after the gene transfer procedure.

Secondary Efficacy Endpoint 5: Absolute lymphocytes on CBC

Absolute lymphocyte counts (ALC) will be determined by routine clinical laboratory complete blood counts (CBC).

Secondary Efficacy Endpoint 6: Absolute number T, B, and NK lymphocytes

Absolute number T, B, NK lymphocytes in peripheral blood will be determined by flow cytometry.

Secondary Efficacy Endpoint 7: Lymphocyte mitogenic proliferation

T lymphocyte proliferative responses to mitogen (phytohemagglutinin – PHA) and to antigens (tetanus toxoid after vaccination and *Candida albicans*) will be determined by tritiated thymidine incorporation or carboxyfluorescein succinimidyl ester (CFSE) labeling by routine clinical laboratory assay.

Secondary Efficacy Endpoint 8: Quantitative immunoglobulins by class

Serum immunoglobulin levels (IgG, IgA and IgM) will be determined by routine clinical laboratory assays. Requirement of immune replacement therapy will be assessed

Secondary Efficacy Endpoint 9: Specific Antibody responses

Serum titers of isohemagglutinin antibodies and antibodies to vaccine antigen tetanus toxoid and to polyribosylphosphate {PRP} will be determined by routine clinical laboratory tests if vaccinations have been administered.

Secondary Efficacy End-point 10: T lymphocyte reconstitution

T lymphocyte production and diversity will be analyzed by measuring PBMC TREC by qPCR and vector integration sites by LAM-PCR, and TCR V β family usage by FACS.

Secondary Efficacy End-point 11: Infection rates will be also measured under immune reconstitution as part of the efficacy assessment of a competent immune system

5 STUDY POPULATION

5.1 Description of the Study Population

Number of subjects to be studied:

A total of twenty (20) subjects will be treated under this protocol. Eligible subjects will be children \geq 1.0 months of age with a diagnosis of ADA-deficient SCID, lacking a medically eligible HLA-matched sibling donor and meeting defined inclusion/exclusion criteria related to medical status and organ function (*vide infra*).

5.1.1 Participant Inclusion Criteria

Inclusion criteria:

Participants must satisfy Inclusion Criteria I, II, and III.

I. Children \geq 1.0 months of age with a diagnosis of ADA-deficient SCID based on:

- A. Decreased ADA enzymatic activity in erythrocytes, leukocytes, skin fibroblasts, or in cultured fetal cells to levels consistent with ADA-deficient SCID as determined by reference laboratory **or** confirmed ADA gene mutation(s) known to cause disease

AND

- B. Evidence of severe combined immunodeficiency based on either:

1. Family history of first order relative with ADA deficiency and clinical and laboratory evidence of severe immunologic deficiency,

OR

2. Evidence of severe immunologic deficiency in subject prior to institution of immune restorative therapy, based on

- a. lymphopenia (absolute lymphocyte count <400 cells/mcL) OR absence or low number of T cells (absolute CD3+ count <300 cells/mcL)

OR

- b. severely decreased T lymphocyte blastogenic responses to phytohemagglutinin (either <10% of lower limit of normal controls for the diagnostic laboratory, <10% of the response of the normal control of the day, or stimulation index <10)

II. Ineligible for matched sibling allogeneic bone marrow transplantation:

Absence of a medically eligible HLA-identical sibling, with normal immune function, who may serve as an allogeneic bone marrow donor.

III. Signed written informed consent according to guidelines of the IRB (UCLA [Office of Human Research Protection Program](#) and National Human Genome Research Institute (NHGRI) Institutional Review Board

5.1.2 Participant Exclusion Criteria

Exclusion criteria:

1. Age \leq 1.0 months

Appropriate organ function as outlined below must be observed within 60 days of entering this trial.

2. Hematologic

- a. Anemia (hemoglobin < 10.5 g/dl at < 2 years of age, or < 11.5 g/dl at > 2 years of age).
- b. Neutropenia: absolute granulocyte count <500/mm³.
- c. Thrombocytopenia (platelet count < 150,000/mm³, at any age).
- d. INR or PT > 2X the upper limit of normal or PTT > 2.33X the upper limits of normal (patients with a correctable deficiency controlled on medication will not be excluded).
- e. Cytogenetic abnormalities on peripheral blood or bone marrow or amniotic fluid (if available).
- f. Prior allogeneic HSCT with cytoreductive conditioning.

3. Infectious

- a. Evidence of infection with HIV-1, hepatitis B, Hepatitis C, or parvovirus B 19 by DNA PCR within 90 days prior to bone marrow harvest. If other infection is present, it must be under control (e.g. stable or decreasing viral load) at the time of screening.

4. Pulmonary

- a. Resting O₂ saturation by pulse oximetry < 95% on room air.
 - b. Chest x-ray indicating active or progressive pulmonary disease.
5. Cardiac
- a. Abnormal electrocardiogram (EKG) indicating cardiac pathology.
 - b. Uncorrected congenital cardiac malformation with clinical symptomatology.
 - c. Active cardiac disease, including clinical evidence of congestive heart failure, cyanosis, hypotension.
 - d. Poor cardiac function as evidenced by LV ejection fraction < 40% on echocardiogram.
6. Neurologic
- a. Significant neurologic abnormality by examination.
 - b. Uncontrolled seizure disorder.
7. Renal
- a. Renal insufficiency: serum creatinine \geq 1.2 mg/dl, or \geq 3+ proteinuria.
 - b. Abnormal serum sodium, potassium, calcium, magnesium, phosphate at grade III or IV by Division of AIDS Toxicity Scale.
8. Hepatic/GI:
- a. Serum transaminases > 5X the upper limit of normal (ULN).
 - b. Serum bilirubin > 2X ULN.
 - c. Serum glucose > 1.5x ULN.
 - d. Intractable severe diarrhea.
9. Oncologic* (see below)
- a. Evidence of active malignant disease other than dermatofibrosarcoma protuberans (DFSP)
 - b. Evidence of DFSP expected to require anti-neoplastic therapy within the 5 years following the infusion of genetically corrected cells
 - c. Evidence of DFSP expected to be life limiting within the 5 years following the infusion of genetically corrected cells
10. Known sensitivity to Busulfan
11. General
- a. Expected survival < 6 months.
 - b. Pregnant.
 - c. Major congenital anomaly.

- d. Ineligible for autologous HSCT by the criteria at the clinical site.
- e. Other conditions which in the opinion of the principal investigator and/or co-investigators, contra-indicate the bone marrow harvest, the administration of busulfan, infusion of OTL-101 or indicate the patient or patient's parents/primary caregivers inability to follow protocol.

* DFSP is a rare, locally invasive tumor with low metastatic potential. Patients receiving active anti-neoplastic therapy for any cancer, including DFSP, are not eligible. Patients with DFSP who are not being treated with active anti-neoplastic therapy at the time of enrollment AND have no plan to receive active anti-neoplastic therapy in the absence of progressive malignant disease AND whose DFSP is not expected to be life-limiting within the five years following the infusion of genetically corrected cells are eligible.

Patients with DFSP, for whom radiation or chemotherapy has been chosen, would remain ineligible during treatment, as the interaction of busulfan and the experimental gene transfer vectors with active anti-neoplastic therapy is difficult to predict and could reasonably be expected to be deleterious due to overlapping toxicities. When anti-neoplastic therapy is concluded, patients with ADA-SCID and a history of DFSP can be included.

